### **7.2.3 ORR: Supportive and Sensitivity Analysis**

ORR will also be analyzed for the modified ITT and PP population, and logistic regression models analogous as defined for OS (see Section 7.1.3) will be made.

In addition, duration of overall response and duration of stable disease will be analyzed by means of time-to-event analysis (see details in section 7.1.2). Duration of overall response is defined for subjects with CR or PR as best overall response as duration from the first time when criteria for a response (PR or CR) were met until first observation of PD. If PD is not reached, the subject is censored at date of last visit with adequate assessment.

Duration of stable disease is defined as duration from start of treatment until first observation of PD for patients with SD as best overall response. If PD is not reached, the subject is censored at date of last visit with adequate assessment. If subject did not receive treatment, date of randomization will be taken as start date.

Moreover, duration of follow-up will be summarized and median duration will also be estimated by means of K-M analysis (i.e. reversing OS censoring).

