7.1.6 Duration of Response

Duration of overall response: The duration of overall response is measured from the time measurement criteria are met for CR or PR (whichever is first recorded) until the first date that recurrent or progressive disease is objectively documented (taking as reference for progressive disease the smallest measurements recorded since the treatment started).

The duration of overall CR is measured from the time measurement criteria are first met for CR until the first date that progressive disease is objectively documented.

Duration of stable disease: Stable disease is measured from the start of the treatment until the criteria for progression are met, taking as reference the smallest measurements recorded since the treatment started, including the baseline measurements.

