### **7.2.4 PFS: Definition**

PFS is defined as the number of days between randomization and the date of progression or death that occurred up to the end of study. PFS for patients who progress and then subsequently die will be the number of days between randomization and the date of progression is first observed.

Progression should be confirmed as specified. PFS data will be censored for subjects whose PFS status cannot be determined. The table below summarized rules of determining the dates of progression and censoring:

Situation	Date of Progression or Censoring	Outcome
No baseline tumor assessments	Randomization	Censored
Progression documented between scheduled visits	Date of the documented progression	Progressed
No progression	Date of last visit with adequate assessment	Censored
Treatment discontinuation for undocumented progression	Date of last visit with adequate assessment	Censored
Treatment discontinuation for toxicity or other reason	Date of last visit with adequate assessment	Censored
New anticancer treatment started	Date of last visit with adequate assessment	Censored
Death between adequate assessment visits	Date of death	Progressed
Death or progression after more than one missed visit	Date of last visit with adequate assessment	Censored

Once the dates of progression, survival, and censoring are derived, PFS will be calculated as follows:

For those who died or progressed up to the end of the study,

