### **12.2.3 Date of Progression or Censoring**

The date of death is the documented date of death. The date of progression (non death) will be determined as follows:

Progression is first observed based on	Date of progression
Unscheduled test prescribed by the investigator based on patients clinical presentation	The date the test is performed

 
Scheduled assessment per protocol
 
	
Assessment done on scheduled visit date + 7 days (Visit Window)	The date of the assessment

 
Assessment done > 7 days after scheduled visit date (Note: this case is not relevant for this trial.)
 
	The date of the next scheduled assessment date after the date of last test indicating no progression. For example, if a patient has an assessment done at Jth scheduled assessment visit with a result no progression and has the next assessment done at (J+4)th scheduled assessment visit (i.e., skipping 4 scheduled assessment visit) with a result showing progression, the date of progression will be the date of (J+1)st scheduled assessment visit.

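### SAP 7.2.3 ends duration of response and duration of stable disease at progression only, so deaths without documented progression are censored and an arm with more of them is not penalised

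*SAP*

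**What the plan says.** SAP 7.2.3 defines duration of response, for patients with CR or PR as best response, "as duration from the first time when criteria for a response (PR or CR) were met until first observation of PD". For the other duration it states: "Duration of stable disease is defined as duration from start of treatment until first observation of PD for patients with SD as best overall response". Each definition is followed by the same rule: "If PD is not reached, the subject is censored at date of last visit with adequate assessment". Death is named neither as an event nor as an exception. Nor can it be read as PD, because SAP Appendix B (12.2.3) keeps the two apart: "The date of progression (non death) will be determined as follows".

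Protocol 7.1.6 has the same end points. Response runs "until the first date that recurrent or progressive disease is objectively documented", and "Stable disease is measured from the start of the treatment until the criteria for progression are met".

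PFS is treated differently. In the table of SAP 7.2.4, the situation "Death between adequate assessment visits" is an event dated at death, and the PFS formula that follows uses progression or death.

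SAP 7.2.3 refers both durations to the methods of SAP 7.1.2: log-rank test, Kaplan-Meier medians and a Cox hazard ratio. Appendix E reports them in Tables 14.2.10 and 14.2.11.

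**The concern.** A responder or stable patient who dies before a scan shows PD leaves the risk set at her last adequate scan. The Kaplan-Meier estimate then treats her as someone who could still have progressed later, at the same rate as those who remain. Death has in fact ended her response, so the curve answers what would happen if nobody died first. The same patient has an event in PFS and a censored time here.

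The consequence is clearest between arms. A death in a stable patient, for example from toxicity, does not shorten the duration estimate of her own arm. If one arm has more such deaths, the comparison by the 7.1.2 methods does not show it, and nothing in SAP 7.2.3 calls for those deaths to be counted beside the estimates.

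**Working it through.** **The plan's own figures.** The documents give no figure for either duration. The one sizing figure, about 384 deaths (SAP 7.5), is reproduced. With HR = 9/12 = 0.75, two-sided 0.05, 80% power and 1:1 allocation, Schoenfeld's formula gives 4 × (1.960 + 0.842)² / (ln 0.75)² ≈ 380 and Freedman's gives 385. The point below does not touch that figure.

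**Inputs**
- End event and censoring rule: SAP 7.2.3.
- Scan interval on treatment: 9 weeks (Protocol 7.1).
- Time scale: median to PD or death of 7 months. This is an assumption, borrowed from the Phase II median time to progression in Protocol 1.2.2.
- f, the share of endings that are deaths without PD: assumed at 5%, 10%, 20% and 30%.

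**Within one arm.** Take constant hazards h_PD and h_D, with f = h_D / (h_PD + h_D).
- Median time to PD or death = ln 2 / (h_PD + h_D).
- Median estimated when deaths are censored = ln 2 / h_PD.
- Ratio of the two = 1 / (1 − f).

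The grid columns simulate 9-weekly scans. PD is dated at the next scan, and a death is either censored at the previous scan (SAP rule) or counted at its date.

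| f | 1/(1−f) | Closed-form median, PD only (PD or death: 7.0) | Grid median, PD only vs PD or death | Kaplan-Meier estimate at 12.5 months, PD only vs PD or death |
|---|---|---|---|---|
| 5% | 1.05 | 7/0.95 = 7.4 | 8.3 vs 8.3 | 0.31 vs 0.29 |
| 10% | 1.11 | 7/0.90 = 7.8 | 8.3 vs 8.3 | 0.32 vs 0.29 |
| 20% | 1.25 | 7/0.80 = 8.8 | 10.4 vs 8.3 | 0.37 vs 0.29 |
| 30% | 1.43 | 7/0.70 = 10.0 | 10.4 vs 8.3 | 0.41 vs 0.29 |

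Medians are in months. A scan interval is 63/30.44 = 2.07 months, so the PD-only grid median can fall only on a scan date: 4 × 2.07 = 8.3 or 5 × 2.07 = 10.4. A shift of 5–11% can therefore vanish in the median while the curve still moves slightly.

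**Between arms.** Let f = 5% in one arm and f = 10%, 20% or 30% in the other.
- Equal hazard of PD or death in both arms: PD-only HR = (1 − f)/0.95 = 0.95, 0.84 or 0.74, in favour of the arm with more deaths without PD.
- Equal hazard of PD in both arms: PD-only HR = 1.0, while the HR for PD or death is 0.95/(1 − f) = 1.06, 1.19 or 1.36 against that arm.

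In the first case the arm looks better than it is. In the second its disadvantage is not shown.

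**The case against.** The strongest reply is that this is a consistent choice and not a slip. Protocol 7.1.6 ends both durations at progression, in a section presented as a summary of RECIST 1.1, and the SAP follows it. A cause-specific time to progression is a legitimate quantity, and it is too long only by comparison with a different endpoint, PD or death. That stands, and it is why the point is worded relative to that endpoint. It does not justify presenting the result as duration of response, with log-rank and Cox comparisons, and no count of deaths beside it.

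It also stands that little depends on these tables. The durations appear under a supportive heading and outside the OS–PFS–ORR testing order of SAP 7.4. They are not among the study objectives in either document.

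The plan contains a partial check. SAP 7.2.6 adds PFS in MITT patients with CR, PR or SD as best response (Table 14.2.16, Figure 14.2.8), under the PFS death rule. It is only partial: it starts at randomization, pools CR, PR and SD, and censors a death after more than one missed visit.

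A reader might infer from the planned median OS of 9 and 12 months that such deaths are common here. The documents do not support that. Those medians describe all patients, whereas f concerns responders and stable patients, and earlier scans are called for when progression is suspected.

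**Conclusion.** The point holds as a modest one. Under SAP 7.2.3 both durations are cause-specific times to progression. Relative to time to PD or death they are too long, and an arm with more deaths without documented PD is not penalised and can look better.

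The size rests on f, for which the documents give no value, and on constant hazards. The median is inflated by about 1.05 at f = 5%, 1.11 at 10% and 1.25 at 20%. On a 9-weekly scan grid with a 7-month median it may not move at 5–10%.

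Three stronger readings are not supported:
- That the trial's main conclusions are at risk. OS, PFS, ORR and the 384-event sizing do not use this rule.
- That the rule favours AEZS-108. Nothing in the documents says which arm would have more such deaths.
- That these patients are shown as having an unending response. They are censored at the last adequate assessment. The fault is what that censoring assumes.

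**What to change.** In SAP 7.2.3, define both durations as time to first documented PD or death from any cause, whichever comes first. Keep the existing censoring at the last adequate assessment for patients who are alive without PD.

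Do not import the PFS table of SAP 7.2.4 wholesale. It censors a death after more than one missed visit, which would contradict death from any cause. It also censors at treatment discontinuation for toxicity or other reason, which may itself be informative.

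Report the number of deaths without documented PD by arm in Tables 14.2.10 and 14.2.11. Align Protocol 7.1.6, or state in the SAP that it departs from it. The PD-only version may stay as a secondary display.

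The cost is a sentence or two of SAP text and one extra row in each of two tables, with no new data and no change to the sample size. The reported durations become somewhat shorter. A death after more than one missed visit will be an event here but censored in PFS, which the SAP should say.

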### **7.2.4 PFS: Definition**

PFS is defined as the number of days between randomization and the date of progression or death that occurred up to the end of study. PFS for patients who progress and then subsequently die will be the number of days between randomization and the date of progression is first observed.

Progression should be confirmed as specified. PFS data will be censored for subjects whose PFS status cannot be determined. The table below summarized rules of determining the dates of progression and censoring:

Situation	Date of Progression or Censoring	Outcome
No baseline tumor assessments	Randomization	Censored
Progression documented between scheduled visits	Date of the documented progression	Progressed
No progression	Date of last visit with adequate assessment	Censored
Treatment discontinuation for undocumented progression	Date of last visit with adequate assessment	Censored
Treatment discontinuation for toxicity or other reason	Date of last visit with adequate assessment	Censored
New anticancer treatment started	Date of last visit with adequate assessment	Censored
Death between adequate assessment visits	Date of death	Progressed
Death or progression after more than one missed visit	Date of last visit with adequate assessment	Censored

Once the dates of progression, survival, and censoring are derived, PFS will be calculated as follows:

For those who died or progressed up to the end of the study,

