- 6) Patients discontinuing study treatment for reasons other than disease progression will be reassessed at 3-month intervals to assess the time to treatment failure (progression / death). Follow-up until progression will be suspended in patients in whom a new cancer treatment has been started without prior documentation of progressive disease. Information on survival status may be captured by telephone if no follow-up visit is scheduled for other reasons.
- 7) If treatment was discontinued because of a drug-related adverse event (i.e., causality at least possibly related), the patient will be followed up as clinically indicated to assess and document the outcome.
- 8) Only required in women of child-bearing potential
- 9) Only a patient developing signs of cardiac failure during post-treatment follow-up will have LVEF and ECG evaluated; a left ventricular dysfunction of CTCAE grade 4 will be reported as an SAE.
- 10) Only anticancer treatments that a patient received during post treatment follow-up for survival will be recorded.
- 11) For tests performed by a laboratory not affiliated to study site (e.g. mid-cycle controls by the patient's home doctor) copies of the external laboratory reports will be provided to the sponsor and results recorded in the CRF.
- 12) A PK sub-study, including electrocardiographic evaluations on Day 1 and Day 2, will be conducted at selected investigational sites. Procedures are described in [APPENDIX 7](#)
- 13) Every effort should be made to start treatment within 4 days of randomization.
- 14) Specimens from FFPE fresh biopsies if FFPE archival tumor specimens are not available.
- 15) Except for Day 1 clinical laboratory tests
- 16) Recommended to be conducted also at end of Cycle 7 and 8 (i.e., before start of Cycle 8 and Cycle 9, respectively) for both arms. Results are to be captured on the eCRF if there is an abnormal finding.
- 17) Sparse PK sampling of AEZS-108 treated patients will be performed at all investigational sites, where feasible. Sparse PK sampling is expected in Cycle 1 or alternatively in a subsequent cycle of ongoing patients, within the following time windows:
 - sample #1: within 60 minutes before end of the 2-hour infusion (during 2nd half of the infusion period);
 - sample #2: between 30 and 60 minutes after the end of infusion (EOI);
 - sample #3: between 120 and 180 minutes after EOI;
 - sample #4 (optional): between 4 and 6 hours after EOI.

TABLE OF CONTENTS

Protocol Authorization.....	2

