7.1.7 Progression-Free Survival (PFS)

PFS is defined as the time elapsed from randomization to the date of documented progression or death, whichever comes first. For surviving patients without progression who begin alternative treatment, PFS will be censored at the last date of documented progression-free status prior to starting alternative treatment. Similarly, losses to follow up will be censored at the last date of documented progression-free status.

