8.6.1 Follow-up until progression

Whenever possible, a patient who has discontinued study treatment for other reason than progressive disease will be followed up at 3-monthly intervals until progression including the following assessments:

- **Clinical assessments** (including ECOG performance status, blood pressure, pulse)
- **Tumor imaging (CT or MRI):** evaluation of time-point response by comparison with target and non-target lesions at time of Best Response
- **Quality of Life:** questionnaires

Anticipated exceptions from follow-up will be “withdrawal of consent”, “lost to follow-up”, “patient moved”.

Follow-ups until progression will be suspended in patients in whom a new cancer treatment has been started without prior documentation of progressive disease. The start date of the new systemic therapy (or local therapy directed to lesions on which response assessment was based) will be documented.

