9.5 Secondary efficacy outcomes

9.5.1 Progression free survival (PFS)

Progression-free survival will be defined as the days between randomization and the date of documented progression or death for any cause. Criteria for disease progression can be found in [Section 7.1.7](#).

For patients whose progression status cannot be determined, their PFS data will be censored at the last adequate progression assessment date that the patient is confirmed to have no progression.

Hypothesis testing between the two treatment arms will be performed using a log-rank test.

For each treatment arm, the median time to progression will be estimated using the Kaplan-Meier method and the 95 % confidence interval of the median will be reported.

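### The SAP's PFS table censors patients who stop treatment for toxicity or other reasons, with no exception for progression or death documented later, contrary to Protocol 7.1.7

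*SAP*

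**What the plan says.** SAP 7.2.4 defines PFS from randomization to progression or death up to the end of the study. It then says "PFS data will be censored for subjects whose PFS status cannot be determined" and gives a table of situations, dates and outcomes. One row is "Treatment discontinuation for toxicity or other reason": censored, at the last visit with adequate assessment. It stands apart from the rows for no progression, for new anticancer treatment and for more than one missed visit. Another row, "Death between adequate assessment visits", counts the death as an event. Neither the table nor SAP Appendix B says which row applies when two fit.

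Protocol 7.1.7 counts documented progression or death, whichever is first. For surviving patients without progression who begin other treatment, "PFS will be censored at the last date of documented progression-free status prior to starting alternative treatment"; losses to follow-up are handled the same way. Protocol 9.5.1 says: "For patients whose progression status cannot be determined, their PFS data will be censored at the last adequate progression assessment date". Neither section gives stopping study treatment as a reason to censor.

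Follow-up continues after a stop. Protocol 8.6.1 says that, whenever possible, "a patient who has discontinued study treatment for other reason than progressive disease will be followed up at 3-monthly intervals until progression". Flow chart footnote 6 and SAP 2.2 and 4.3 agree.

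**The concern.** The row requires no new therapy, no loss to follow-up, no missed visit and no absence of a later event. On its plain wording, a patient who stops for toxicity and progresses on the next scheduled scan is censored before that scan. The trial collects the event and the analysis then drops it.

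PFS is a key secondary endpoint, tested second in the hierarchy and intended for labeling claims (SAP 7.4). Two programmers could derive different PFS event counts from the same data. If the row overrides later events, power is lost. The hazard ratio can also be distorted if stopping is related to prognosis and differs between arms. That is plausible because the trial is open-label and withdrawal may rest on the investigator's judgment (Protocol 5.3). None of the PFS analyses in SAP 7.2.6 removes this censoring: they change the population, take a subset by best response, or add covariates.

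**Working it through.** **1. Two patients put through the rules.**

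Patient A responds, stops for toxicity, starts no new therapy, misses no visit, and progresses on a 3-monthly scan.

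| Rule | Result |
|---|---|
| Protocol 7.1.7 | Event at the scan |
| Protocol 9.5.1 | Status is determined, so event |
| SAP 7.2.3, duration of response ("If PD is not reached, the subject is censored at date of last visit with adequate assessment") | PD is reached, so event |
| SAP 7.2.4, discontinuation row | Censored |

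The same scan is an event for duration of response and is lost for PFS.

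Patient B stops for toxicity and dies before the next scan. On the face of the table, two rows fit: the death row (event) and the discontinuation row (censored). Nothing ranks them.

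**2. Does the milder reading rescue the row?** Suppose it covers only patients with no documented event. Those patients already fall under the no-progression row, with the same date and outcome. The row then adds nothing; it does separate work only if it overrides later events.

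**3. Size (illustration).** The plan gives no PFS event count or PFS power, so there is no stated PFS figure to reproduce. The 384 deaths concern OS and are not in question.

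*From the documents:* 500 patients, 1:1; 24 months' accrual plus 12 months' follow-up; up to 9 cycles of 21 days, so 189/30.44 = 6.2 months.

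*Assumed:* exponential PFS with median 3–6 months in both arms; 10% in one arm and 20–30% in the other who would stop within 6.2 months if they had no PFS event; 0, 50% or 80% of stoppers starting new therapy at the stop; post-stop hazard 1, 1.5 or 2 times the on-treatment hazard. The comparator is the protocol rule, which still censors at new therapy.

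*Events without the row, median 4 months, no new therapy.* With λ = ln 2/4 = 0.1733, expected events are 500 × [1 − (e^(−12λ) − e^(−36λ))/(24λ)] = 485.

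*Share stopping before an event.* With stop hazard h = −ln(1 − p)/6.2, the share is h/(h + λ) × [1 − e^(−6.2(h + λ))]:

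| p | h per month | Share stopping first |
|---|---|---|
| 10% | 0.0170 | 6.2% |
| 20% | 0.0359 | 12.5% |
| 30% | 0.0574 | 19.0% |

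The average is 9.3% of patients for 10% vs 20%, and 12.6% for 10% vs 30%. Simulation, which adds end-of-study censoring, gives 441 and 425 events: losses of 44/485 = 9.1% and 60/485 = 12.4%.

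*Power for an assumed PFS HR of 0.80*, Φ(√(d/4) × |ln 0.80| − 1.96): 69% with d = 485, 65% with d = 441, 63% with d = 425.

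*Events lost over all medians (simulation):*

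| Stoppers starting new therapy | PFS events lost |
|---|---|
| 0 | 8–15% |
| 50% | 4–8% |
| 80% | 2–4% |

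*Hazard ratio, AEZS-108 to doxorubicin*, median 4 months, equal on-treatment hazards, post-stop hazard 1.5 to 2 times higher:

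| Stopping, AEZS-108 vs doxorubicin | New therapy | Protocol rule | SAP row |
|---|---|---|---|
| 10% vs 30% | 0 | 0.96–0.93 | 1.00 |
| 10% vs 30% | 50% | 0.97–0.96 | 1.00 |
| 10% vs 30% | 80% | 0.99–0.98 | 1.00 |
| 30% vs 10% | 0 | 1.05–1.07 | 1.00 |
| 30% vs 10% | 50% | 1.03–1.04 | 1.00 |
| 30% vs 10% | 80% | 1.01–1.02 | 1.00 |

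With equal stopping rates, or no change in hazard after the stop, the hazard ratio is not biased and the cost is power only.

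**The case against.** The best defence is that the row was never meant to override an event. Its lead-in limits censoring to undeterminable status, and Appendix B speaks of a censoring date for patients who never progressed. When the table does censor a documented event, in the missed-visit row, it names death or progression; this row names neither. The date column does not say before discontinuation. Protocol 9 also leaves censoring details to the SAP.

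Part of this stands. The milder reading is possible. If it were written down, a death or progression after stopping would simply leave the row, and nothing would be lost. Redundancy alone proves little, since the row for undocumented progression overlaps the no-progression row in the same way.

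It does not settle the matter. The new-anticancer-treatment row is equally bare, uses the same date wording, and is meant to override later events, as Protocol 7.1.7 shows. A programmer has no textual reason to treat the discontinuation row differently. Freedom to detail censoring does not explain a rule that conflicts with Protocol 7.1.7 and with the SAP's own lead-in.

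The figures rest on assumptions. The only related number in the documents is a Phase II median TTP of about 7 months, in patients of whom 10 of 43 had prior chemotherapy. At that median the formula above gives 7.5% and 15.0% stopping first for p = 10% and 20%, so a longer median does not shrink the problem. Heavy use of new therapy does. PFS can also be claimed only if OS succeeds.

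**Conclusion.** The concern holds. As written, the row conflicts with Protocol 7.1.7 and 9.5.1, with its own lead-in and with the SAP's duration-of-response rule, and no precedence rule resolves it. This is a defect in the text; it does not show that the programming drops events.

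Under the override reading, and on the assumptions above, roughly 2–15% of PFS events are lost, depending mainly on how many stoppers start new therapy. Any shift in the hazard ratio needs both unequal stopping and a changed hazard after stopping, and the documents do not fix its direction. Under the milder reading no events are lost, but that reading must be stated. Patients who complete nine cycles are not part of the point, because Protocol 5.3 treats withdrawal from treatment as premature discontinuation. Primary OS is unaffected. It should be fixed.

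**What to change.** In SAP 7.2.4:

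- Delete the row, or limit it to patients with no later documented progression or death.
- State that stopping study treatment does not by itself censor PFS. Later progression or death counts at its own date unless new anticancer therapy has started or more than one visit was missed.
- Apply the same rule to the row for discontinuation with undocumented progression.
- State the order of precedence among the rows.

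If censoring at treatment stop is wanted, put it in SAP 7.2.6 as a labelled sensitivity analysis.

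The cost is SAP wording and one derivation, before database lock. The off-treatment scans and deaths are already collected.
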